Master or doctoral level social workers or psychologists will conduct the clinical screens to assess participant eligibility. All recruitment will take place at Integrity House. Staff will be supervised by our co-investigator project director and the PI [name].

Inclusion criteria for the factorial experiment participants in the study will include:

- Men age 18 or older
- Residence in Essex County, NJ
- Willingness to be voice recorded during group sessions
- Ability to speak English
- Having a substance use disorder measured by the Global Appraisal of Individual Needs-Substance Problem Scale (GAIN-SPS).
- Having been released from incarceration in the past 4 years. This is due to research that shows that people are more likely to be re-incarcerated within the first 4 years of release from incarceration.

Exclusion criteria for RCT participants will include:

- Severe psychiatric disorders in the prior 6 months not stabilized (schizophrenia, depression with psychotic features, bipolar disorder, any psychosis), as measured by the MINI International Neuropsychiatric Interview 6 psychosis and suicidality modules
- Gross cognitive impairment as measured by the Mini Mental State Exam.
- Sexual identification as female

Inclusion criteria for the focus group participants in the study will include:

- Being randomly selected from the study's intent to treat sample
- Being willing to be voice recorded
- Having attended at least one intervention session

Inclusion criteria for the NCCB members include:

- Men and women age 18 or older
- Knowledge about Essex County, NJ
- Ability to speak English
- Being invited to become a NCCB member after a majority favoring vote

We will use a screening script and a signed consent form to obtain permission to conduct the screening and use the data as part of the study, regardless of establishment of final eligibility.

Participants will be informed that the information will be confidential and they can choose to stop participating at any time and we will destroy their data upon receiving their request. Note that voice recordings of Community Wise are exceptions as this will include data from entire groups of participants. We will only destroy voice recordings if there is reason to believe the recording has content that can put participants in danger of being hurt or re-incarcerated.

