 - a. Possible discomfort from answering personal questions. If the participants experience such discomfort at any time, they are free to inform the interviewer or facilitator, and are free to withdraw from the program. Interviewers will be trained to observe signs of discomfort and check with participants if they want to continue. Licensed facilitators and peer facilitators are trained to address discomfort during the sessions and participants are able to leave whenever they need.
 - b. Discomfort or risk of minor or major substance withdrawal symptoms. This will be carefully assessed at the Clinical Screen and throughout the intervention. Monthly assessments will test levels of AIDU and suicidality. Staff at Integrity House, Inc. and NJCRI, as well as group facilitators are highly trained to recognize and recommend courses of action for current or potential withdrawal symptoms, and will consult with project director at Integrity House, Inc. Integrity House, Inc. offers a variety of substance abuse treatment services and staff there are fully trained to recognize and address signs of withdrawal. [name] will be available to consult with project director and the group facilitators via phone and e-mail, and she will provide on-going, remote clinical supervision and monitoring of each case. In the event of acute withdrawal symptoms or high risk behaviors (i.e., suicidal or homicidal ideation, intent, or plan), the facilitator will refer the participant to the appropriate staff at NJCRI for admission to inpatient or ambulatory detoxification. [name] and the project director will review each intake for risk of withdrawal symptoms, level of care needs, and appropriate action plan. Members of the NCCB who are service providers will be available to provide consultation to any challenges that may arise with participants. Member service providers include social workers experienced in the field of substance abuse.

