In the past year, did you use any drugs or drank any alcohol? _____

Yes
 No

GAIN SPS-SII

Next we want to go over a list of common problems related to alcohol. After each of the following questions, we would like you to tell us the last time you had this problem.

	Past Month (3)	Past year (2)	Lifetime (1)	Never (0)
c. c. When was the last time that you tried to hide that you were using alcohol or other drugs?				
d. d. When was the last time that your parents, family, partner, co-workers, classmates or friends complained about your alcohol or other drug use?				
e. e. When was the last time that you used alcohol or other drugs weekly or more often?				
f. f. ... your alcohol or other drug use caused you to feel depressed, nervous, suspicious, uninterested in things, reduced your sexual desire or caused other psychological problems?				
g. g. ...your alcohol or other drug use caused you to have numbness, tingling, shakes, blackouts, hepatitis, TB, sexually transmitted disease, or any other health problems?				
h. h. ... you kept using alcohol or other drug even though you knew it was keeping you from meeting your responsibilities at work, school, or home?				
j. j. ...you repeatedly used alcohol or other drugs when it made the situation unsafe or dangerous for you, such as when you were driving a car, using a machine, or when you might have been forced into sex or hurt?				
k. k. ...your alcohol or other drugs caused you to have repeated problems with law?				
m.				

m. ... you kept using alcohol or other drugs even though it was causing social problems, leading to fights, or getting you into trouble with other people?

n. n. ... you needed more alcohol or other drugs to get the same high or found that the same amount did not get you as high as it used to?

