p. p. ... you had withdrawal problems from alcohol or other drugs like shaky hands, throwing up, having trouble sitting still or sleeping, or you used any alcohol to stop being sick or avoid withdrawal problems?

q. q. ...you used alcohol or other drugs in larger amounts, more often or for a longer time than you meant to?

r. r. ...you were unable to cut down on or stop using alcohol or other drugs?

s. s. ... you spent a lot of time either getting alcohol or other drugs , using alcohol or other drugs , or feeling the effects of alcohol or other drugs (high, sick)?

t. t. ... your use of alcohol or other drugs caused you to give up, reduce or have problems at important activities at work, school, home or social events?

u. u. ...you kept using alcohol or other drugs even after you knew it was causing or adding to medical, psychological or emotional problems you were having?

ua. ua. ... you wanted to use alcohol or other drugs so badly you couldn't think of anything else?

GAIN Substance use disorder

Number of symptoms coded 2 (past year) for Alcohol _____

Number of symptoms coded 1 (lifetime) for Alcohol _____

Number of symptoms coded 2 (past year) for heroin _____

Number of symptoms coded 1 (lifetime) for heroin _____

Number of symptoms coded 2 (past year) for cocaine _____

Number of symptoms coded 1 (lifetime) for cocaine _____

Number of symptoms coded 2 (past year) for cannabis _____

Number of symptoms coded 1 (lifetime) for cannabis _____

Number of symptoms coded 2 (past year) for opiates _____

Number of symptoms coded 1 (lifetime) for opiates _____

Number of symptoms coded 2 (past year) for downers _____

Number of symptoms coded 1 (lifetime) for downers _____

Number of symptoms coded 2 (past year) for hallucinogens _____

Number of symptoms coded 1 (lifetime) for hallucinogens _____

What is the participant's substance use disorder diagnosis (2 or more symptoms in the specific time frame)?

None
 Past year
 Lifetime

FOR CLINICIAN TO ANSWER: Did the participant have a SUD disorder lifetime or past year AND used drugs last year OR met the weekly use threshold?

Yes
 No

The Clinical Screening is complete.

The candidate is ELIGIBLE to participate in Community Wise Optimization study. Please notify the candidate about the result and proceed to next step to enroll the candidate as a participant of our study. Feel free to make any notes in the below section.

Make sure you press the SUBMIT button before closing your browser!

Field Note

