keep using alcohol or other drugs even though it was causing social problems, leading to fights, or getting you into trouble with other people?

n need more alcohol or other drugs to get the same high or found that same amount did not get you as high as it used to?

p have withdrawal problems from alcohol or other drugs like shaky hands, throwing up, having trouble sitting still or sleeping, or you used any alcohol or other drugs to stop being sick or avoid withdrawal problems?

q use alcohol or other drugs in larger amounts, more often or for a longer time than you meant to?

r were you unable to cut down on or stop using alcohol or other drugs?

s spend a lot of time either getting alcohol or other drugs, using alcohol or other drugs, or feeling the effects of alcohol or other drugs (high, sick)?

t your use of alcohol or other drugs caused you to give up, reduce or have problems at important activities at work, school, home or social events?

u keep using alcohol or other drugs even after you knew it was causing or adding to medical, psychological or emotional problems you were having?

ua have such strong urges to use alcohol or other drugs you could not think of anything else?

When was the last time you...

	Never	1+years ago	4 to 12 months ago	2 to 3 months ago	Past month
a. had a disagreement in which you pushed, grabbed, or shoved someone?					
b. took something from a store without paying for it?					
c. sold, distributed, or helped to make illegal drugs?					
d. drove a vehicle while under the influence of alcohol or illegal drugs?					
e. purposely damaged or destroyed property that did not belong to you?					

How ready are you now to remain abstinent from (not use) alcohol, marijuana, cocaine, heroin and other drugs?

(Place a mark on the scale above)

When was the last time you smoked or used any kind of tobacco? Please include cigarettes, cigars, chewing tobacco and pipes.

- Never
- More than 12 months ago
- 4 to 12 months ago
- 1 to 3 months ago
- 1 to 4 weeks ago
- 3 7 days ago

During the past 30 days, on how many days have you smoked or used any kind of tobacco?

On those days, how many times per day did you usually smoke or use any kind of tobacco? (NOTE: A pack of cigarettes would be about 20 times)

Do you have any physical problems with your vision, hearing, limbs or any other problems communicating or getting around?

	Yes	No

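### At the clinical screen, the GAIN lead-in and the relief-use clause of the withdrawal item name only alcohol, which conflicts with the baseline form and with the screen's own by-substance tallies

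*Combined protocol and SAP*

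**What the plan says.** **Role of the form.** Section 9 makes the GAIN Substance Problem Scale the measure of the substance use disorder inclusion criterion. The Clinical Screening Survey sets the diagnosis at two or more symptoms in a time frame. It asks for the count separately for alcohol, heroin, cocaine, cannabis, opiates, downers and hallucinogens, for example "Number of symptoms coded 2 (past year) for heroin".

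**Wording at the screen (GAIN SPS-SII grid).** The lead-in is "Next we want to go over a list of common problems related to alcohol". Item p has two clauses. The symptom clause covers all substances: "you had withdrawal problems from alcohol or other drugs like shaky hands, throwing up". The relief clause does not: "or you used any alcohol to stop being sick or avoid withdrawal problems".

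**Wording at baseline (Baseline Survey, GAIN, item p).** The relief clause is "or you used any alcohol or other drugs to stop being sick or avoid withdrawal problems".

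**Reliance on the screen.** The Data and Safety Monitoring Plan in section 20C, item 2b, lists withdrawal symptoms as a study risk and says: "This will be carefully assessed at the Clinical Screen and throughout the intervention". The same item adds a review of each intake for withdrawal risk.

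**The concern.** One item of one instrument is worded in two ways, and the narrower wording is on the form that decides entry. An alcohol-only screen does not appear to be intended. Every grid item names other drugs somewhere, and the form then asks for drug-specific counts. A relief clause that names only alcohol cannot supply a heroin, opiate or downer symptom, so the form asks for counts that its own wording does not fully collect.

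The men affected are those who use a drug regularly enough to prevent withdrawal. Such a man can truthfully answer never, or give an older date, at the screen and then answer yes at baseline. Item p is the only question in the screening survey that asks about withdrawal by name, so the omission bears directly on the assessment promised in the safety plan. The effect on eligibility scoring is secondary.

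**Working it through.** The plan states no figure on this point. The check compares the wording of the two forms and applies the two-symptom rule by hand.

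**Step 1: count the items.** The screen grid has items c, d, e, f, g, h, j, k, m, n, p, q, r, s, t, u and ua, which makes 17. All 17 name drugs other than alcohol at some point. Only item p contains a clause restricted to alcohol, and only item p mentions withdrawal by name.

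**Step 2: compare item p across the forms.**

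| Man's situation | Screen, item p | Baseline, item p |
|---|---|---|
| Withdrawal symptoms from any substance | Counted | Counted |
| Drinks alcohol to avoid withdrawal, no symptoms | Counted | Counted |
| Takes heroin, opiates or downers to avoid withdrawal, no symptoms | **Not counted** | Counted |

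The screen records how recently each problem occurred, and baseline asks about the past 30 days. Only the third row differs because of the item's wording.

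**Step 3: effect on the diagnosis.** Let S be the number of symptoms counted among the other 17 − 1 = 16 items, for one substance and time frame. The count is S when item p is missed and S + 1 when it is credited. The threshold is 2.

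| S | Item p missed | Item p credited | Diagnosis changes? |
|---|---|---|---|
| 0 | 0 | 1 | No |
| 1 | 1 | 2 | **Yes** |
| 2 or more | 2 or more | 3 or more | No |

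The diagnosis therefore changes only when S = 1.

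**Step 4: effect on entry.** The final clinician question combines three conditions without brackets: a disorder (lifetime or past year), past-year use, and the weekly-use threshold. That threshold is 4 or more days of any drug, or 4 or more days of binge drinking, in the past month.

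- Read as (disorder AND past-year use) OR weekly threshold, a man with 4 or more drug-use days enters whatever his symptom count.
- Read as disorder AND (past-year use OR weekly threshold), a lost symptom can matter, but only when S = 1 and no other substance or time frame gives him a diagnosis.

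**The case against.** The case that this is only a copy-editing slip is strong, and most of it stands.

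- **The lead-in.** A reader might infer that an alcohol-only introduction lowers the scores of drug-only users on all 17 items. The documents do not support that. Each item names other drugs. The grid follows drug-by-drug Timeline Follow Back questions and is given in person by clinicians or trained senior staff. The counts by substance also require someone to establish which drug each symptom belongs to.
- **Entry.** A man dosing to stay well would very likely meet the weekly-use threshold. He also has 16 other items on which to score, including weekly use, tolerance, inability to stop and time spent using. Exactly one other symptom would be unusual for him.
- **Safety.** A reader might infer that the intake review receives a false negative. That treats item p as the review's only input. The same screen records days and typical amounts of heroin, prescription opiates and downers. Item g mentions shakes and item s mentions feeling sick. The safety plan adds monitoring during the intervention, and the fuller item p is asked at baseline, before groups start.
- **Trial results.** A reader might infer bias in the outcome, since the outcome is alcohol and illicit drug use. The screen precedes randomization and is the same form for every condition, so a missed symptom cannot depend on the condition assigned.

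Two things remain. The two forms contradict each other on item p. The screen's one direct withdrawal question also omits use of drugs to avoid withdrawal. The Timeline Follow Back records how much is used, not whether it is used to stay well.

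**Conclusion.** The point holds as an inconsistency in a working eligibility form with a limited practical effect. The screen lead-in and the relief clause of item p conflict with the baseline form and with the screen's own by-substance counts. The affected man is one who takes heroin, opiates or downers to avoid withdrawal and reports no withdrawal symptoms. He can be missed on the single screening item that names withdrawal, and other parts of the screen, the intake review and the baseline form reduce that gap.

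Item p costs at most 1 symptom of 17. A changed eligibility decision requires S = 1 and, on one reading of the entry rule, use below the weekly threshold as well. It should be rare, but that is a judgement from the item content, because the documents give no symptom distribution from which to estimate it. There is no bias in the comparison between conditions. The conclusion assumes that the items are read out as printed. If screeners already add drugs to the relief clause in practice, the effect is smaller still.

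**What to change.** In the Clinical Screening Survey, extend the GAIN lead-in to cover alcohol or other drugs, and replace the relief clause of item p with the wording already used in the Baseline Survey. Apply the revised form from the next man screened, and store a form-version field with the screening data.

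The cost is two text edits in REDCap and one IRB form revision. No threshold, visit or clinical procedure changes. The downside is a small version change in screening scores between waves, which the version field makes visible. If screening is already complete, note the difference in item p wherever screen and baseline GAIN responses are compared or reported.

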Determine if psychotic symptoms are due to drug use

Do these psychological problems happen only when or after you have been using alcohol or other drugs?
 
Do these psychological problems happen even when you have not been using alcohol or other drugs?
 
DO NOT ASK THIS, USE YOUR JUDGMENT TO ANSWER: Are psychotic symptoms drug induced?
 
Does participant have psychotic symptoms that are likely to intervene with participation in Community Wise?
	 Yes  No

Clinician notes to support their recommendation.
	

(Notify participant that if they seek treatment for these symptoms they can become eligible in the future.)

Timeline Follow Back Alcohol Use Questions

Number of days on which alcohol was used in the past 30 days.
	<hr/>

Average number of drinks per drinking day in past 30 days. (NOTE: MUST WRITE 1 DECIMAL PLACE, e.g. 0.0). To get this number, add the total number of drinks in the month, then divide it by the number of drinking days.
	<hr/>

Number of heavy drinking days. (Heavy Drinking = 4 or more drinks in one occasion) _____

Timeline Follow Back Drug use questions

Number of days on which heroin was used in the past 30 days. _____

How much heroin do you typically use in a day? _____

Number of days on which cocaine was used in the past 30 days. _____

How much cocaine do you typically use on a day? _____

Number of days in which cannabis was used in the past 30 days. _____

How much cannabis do you typically use on a day. _____

Number of days on which prescription opiates was used in the past 30 days. _____

How much prescription opiates do you typically use on a day. _____

Number of days on which prescription downers (Benzos, Barbiturates) was used in the past 30 days. _____

How much prescription downers do you typically use on a day. _____

Number of days on which hallucinogens was used in the past 30 days? _____

How much hallucinogens do you typically use on a day? _____

Number of days on which synthetic marijuana was used in the past 30 days? _____

How much synthetic marijuana do you typically use on a day? _____

Number of days in which other drug was used in the past 30 days _____

How much other drugs do you typically use a day? _____

Specify other drug _____

Did the participant meet the weekly use in the past month threshold? (4 or more days using any drug or 4 or more days of binge drinking) _____

Yes
 No

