The participant is NOT ELIGIBLE at this time.

Reason ineligible at clinical screening.

- More than 3 No shows for scheduled interview
- Mini-mental score
- Suicidality criteria
- Psychoticism criteria
- Alcohol usage criteria
- Substance usage criteria
- Refused
- Other Reason

Explain the reason for ineligibility at clinical screening.

Script for terminating the Clinical Screen:

If they do not qualify:

I am sorry but the screen is showing you are not eligible. The intervention has some components that could be more harmful to some people. Since the program is still new, we are not taking any risks and making sure your safety comes first. If ineligible due to MINI, let them know the screen captured a cognitive deficit and encourage them to contact their doctor for further screening. If they ask what that means, say they do not seem to be processing information properly. This could be due to an injury, age, genetics, drug use, or other illnesses. Thus, they should follow up with a doctor. If they are ineligible due to their drug use level, tell them their level of substance use disqualified them but do not provide further information. Refer them appropriately with the referral list.

If they say they are seeking residential treatment, let them know they do not qualify for the study. If they say they tried to get into residential but were unable to, ask how long the waiting list is. If longer than 5 months, admit them. If not, let them know they are not eligible.

If they qualify:

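### As printed, the screening form's symptom tallies omit past-month symptoms, and its unbracketed eligibility item has one reading that admits men without the required disorder

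*Combined protocol and SAP*

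**What the plan says.** Section 9 (Inclusion and exclusion criteria) makes a substance use disorder on the GAIN-SPS an entry requirement. It gives no alternative route based on how often a man uses.

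The Clinical Screening Survey puts that requirement into practice in four steps:

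- **Use.** The Timeline Follow Back questions define a weekly threshold as "4 or more days using any drug or 4 or more days of binge drinking" in the past month. A further question asks "In the past year, did you use any drugs or drank any alcohol".
- **Symptom grid (GAIN SPS-SII).** Each item takes one code by last occurrence: past month 3, past year 2, lifetime 1, never 0. The items ask about alcohol and other drugs together.
- **Tallies (GAIN Substance use disorder).** Two lines for each of seven substances count symptoms by code. The first is "Number of symptoms coded 2 (past year) for Alcohol", and its partner counts symptoms coded 1 as lifetime. The diagnosis item then applies the standard "2 or more symptoms in the specific time frame", with the answers None, Past year or Lifetime.
- **Eligibility.** The clinician answers "Did the participant have a SUD disorder lifetime or past year AND used drugs last year OR met the weekly use threshold".

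**The concern.** There are two separate faults in the wording.

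First, the grid has four codes and the tallies use two of them. No line counts code 3, and no printed instruction adds code 3 to code 2. The symptoms left out are the most recent ones. A man whose problems are all current could be tallied as having none.

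Second, the eligibility item can be bracketed in two ways, and the two rules differ. Under one of them, frequency of use alone is enough. That contradicts Section 9, and also Section 10, which describes the men to be randomised as having substance use disorders.

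At stake is the make-up of the enrolled sample, and so the population to which the component effects apply.

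**Working it through.** No sample-size or power figure is involved. The check sets the form's rules against each other.

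**1. Form counts.** Grid items c, d, e, f, g, h, j, k, m, n, p, q, r, s, t, u and ua make 17. Tally lines: 7 substances × 2 = 14, of which 0 name code 3.

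**2. Tally against time frame.** Take one substance. The literal rule gives Past year if at least 2 symptoms are coded 2, otherwise Lifetime if at least 2 are coded 1, otherwise None. The diagnosis item's time frame implies something else. Past month lies within past year, and both lie within lifetime, so past year means codes 2–3 and lifetime means codes 1–3.

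| Pattern | Coded 2 | Coded 1 | Literal result | Codes 2–3 | Codes 1–3 | Result by time frame |
|---|---|---|---|---|---|---|
| 17 coded 3 | 0 | 0 | None | 17 | 17 | Past year |
| 2 coded 3 | 0 | 0 | None | 2 | 2 | Past year |
| 16 coded 3, 1 coded 2 | 1 | 0 | None | 17 | 17 | Past year |
| 15 coded 3, 2 coded 1 | 0 | 2 | Lifetime | 15 | 17 | Past year |
| 1 coded 2, 1 coded 1 | 1 | 1 | None | 1 | 2 | Lifetime |
| 2 coded 2 | 2 | 0 | Past year | 2 | 2 | Past year |

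The two rules agree only in the last row, where no symptom is coded 3 and the codes are not mixed.

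**3. Eligibility item.** Let S = disorder, U = past-year use and W = weekly threshold. Reading A is (S AND U) OR W. Reading B is S AND (U OR W).

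| S | U | W | A | B |
|---|---|---|---|---|
| 0 | 0 | 0 | no | no |
| 0 | 0 | 1 | **yes** | **no** |
| 0 | 1 | 0 | no | no |
| 0 | 1 | 1 | **yes** | **no** |
| 1 | 0 | 0 | no | no |
| 1 | 0 | 1 | yes | yes |
| 1 | 1 | 0 | yes | yes |
| 1 | 1 | 1 | yes | yes |

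The readings differ in 2 of 8 rows, exactly where S = 0 and W = 1. W is a count of days and contains no symptom criterion, so A admits men without the disorder and B does not.

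The meaning of drugs in the final item also matters. If it includes alcohol, as the past-year use question does, W implies U. The rows with U = 0 and W = 1 then cannot occur, and the OR clause changes nothing under B. If it excludes alcohol, the clause has work to do under B: it brings in a man with an alcohol disorder who meets the binge-drinking threshold.

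**4. The two faults together.**

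- Heroin on 20 days, 11 items coded 3: the literal tallies are 0 and 0, so S = 0, with U = 1 and W = 1. He is accepted under A and rejected under B. Counting codes 2–3 gives S = 1, and both readings accept him.
- Cannabis on 4 days, only item e coded 3: 1 symptom at most, so S = 0 however code 3 is treated. He is accepted under A only. Relabelling the tallies does not settle this case; the investigators' rule must.

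**The case against.** The strongest reply is that the form may never have been scored literally. The diagnosis item does not tell the clinician to rely on the tallies, and its time-frame wording already takes in past-month symptoms. The grid pools alcohol and drugs, so the per-substance lines cannot be filled from it alone. The Clinical Screen Packet Checklist includes a separate GAIN scale, Section 15 lists the GAIN among the attached screening measures, and Table 1 refers to its first two pages. That sheet is not visible here and may use other codes. Sections 9 and 10 assign the screen to qualified, trained staff. The survey is also a printout of an electronic form, whose display logic is not shown. Finally, reading B agrees with Section 9.

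All of this stands as a limit on the claim. A reader might infer that current cases were turned away or that men without a disorder were enrolled. The documents show neither. A reader might also take three other features as errors: two old lifetime symptoms can qualify, the ineligibility list contains usage reasons, and synthetic marijuana and other drugs have no tally line. None is shown to be one. Section 9 sets no time frame and the form offers a Lifetime answer; the reasons may simply be labels for failing a criterion; and synthetic marijuana, for example, may be tallied under cannabis.

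The reply does not remove the mismatch between the printed tally labels and the diagnosis item. Nor does it say which bracketing applies.

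**Conclusion.** The point holds as a fault of wording. None of the 14 tally lines counts past-month symptoms, which conflicts with the form's own time-frame standard, and one of two readings of the final item contradicts Section 9. The worked patterns assume literal scoring with all symptoms attributed to one substance.

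The number of men affected cannot be computed from the documents. A reader might infer bias in the factorial comparisons. That does not follow: Section 8A-1 settles eligibility before consent and randomisation, so any misclassification at screening is unrelated to assigned condition. The effect is limited to who is enrolled and to whom the results apply. It is a minor point for the investigators to consider.

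**What to change.** - **Tallies.** Label the past-year line as codes 2–3 and the lifetime line as codes 1–3.
- **Eligibility item.** Reconcile Section 9 with the final clinician item on whether a disorder is required or weekly use alone suffices, and on whether drugs includes alcohol as in the past-year use question. Then bracket the item to match. The investigators must state which rule was intended.
- **If screening has closed.** The Certificate of Confidentiality gives an expected end of 12/31/2019, while approval stamps carry the date November 15, 2021, so the documents do not settle this. State the rule that was used, and cross-tabulate grid symptom counts (codes 2–3 and codes 1–3) against recorded diagnosis and eligibility. Say whether item e, "When was the last time that you used alcohol or other drugs weekly or more often", is counted, since it asks about frequency of use. Adding one other past-month symptom to the cannabis example gives 2 of 17 items with item e and 1 of 16 without it.

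Present the table as descriptive and approximate: one alcohol symptom and one cannabis symptom give a pooled count of 2 without 2 for either substance. For that reason it should not be used to exclude anyone, and all randomised men stay in the analysis.

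The cost is a form edit and a short screener briefing if screening is open, with the form version recorded if it changes between waves. Otherwise it is one table from items already collected. Recruitment may slow if weekly use alone had been accepted and the stated rule no longer allows it.
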